Infusion via each catheter will be initiated at the rate of 3 μ L/min/catheter and gradually increased in a stepwise manner. The infusion flow rate can be adjusted at the discretion of the Investigator during real time MRI (with subject maintained under anesthesia) provided that the flow rate per catheter does not exceed 10 μ L/min. All functioning catheters should be convecting at similar flow rates. The flow rate should be established such that the duration of infusion is at least 24 hours to a maximum of approximately 48 hours. In the event only one catheter is functioning the flow rate may be increased to complete infusion in 48 hours or less but greater than 24 hours. After the real-time MRI infusion monitoring period is completed, the remainder of the infusion will continue with the subject awake. MRI will be performed upon completion of infusion as a final evaluation of MDNA55 infusate distribution.

Post-treatment follow-up assessment of safety will be performed 14 days after CED infusion. Thereafter, efficacy and safety assessments will be performed at 30, 60, 90 and 120 days after CED infusion and every 8 weeks thereafter until 360 days of active follow up have been completed. Subjects who discontinue before the Day 360 visit will undergo all the procedures scheduled for the Day 360 visit at the time of discontinuation (see section 7.5.4 for specific details concerning early termination visit).

Subjects who complete the Day 360 assessment without disease progression or who discontinue early without disease progression will continue to be followed for disease status until progression. After progression (on study or during post-study follow-up), subjects will continue to be followed for survival and post-study treatment(s) for GB and imaging for GB until death (or termination of data collection by the Sponsor or withdrawal of consent by the subject).

4 Study Population

The population for this study will consist of subjects with histologically proven primary (*de novo*) GB that has recurred or progressed (per RANO criteria) after treatment(s) including surgery and radiotherapy with or without chemotherapy (according to local practice; Stupp protocol, Stupp *et al.*, 2005) and following discontinuation of any previous standard or investigational lines of therapy (up to 2 prior lines of therapy).

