7.2.3 Pharmacokinetic and Immune Parameter Evaluations

Systemic exposure to MDNA55 is not expected following intra- and peritumoral infusion and circulating MDNA55 has not been detected in previous clinical studies. To continue to evaluate the potential of systemic exposure, blood samples will be collected for analysis at the times indicated in Table 7.

Blood samples will also be collected for testing for the presence of antibodies against MDNA55 (Table 7). If serum anti-MDNA55 antibodies are present, further immunogenicity assessments will be carried out for determination of antibody neutralization potential. Other immune parameters may also be assessed.

All collected blood samples will be processed according to a laboratory manual and samples will be stored at -70°C until instructions are provided to the site to ship the samples to the central testing laboratory (MicroConstants Inc., San Diego, CA).

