- g3 On Day 0 MRI performed following catheter placement prior to the start of CED infusion as well as during infusion for real-time MRI infusion monitoring (for approximately 1 hour while subject is maintained under anesthesia) (see Section 6.3 for CED infusion procedure)
- 94 On Day 1 or Day 2 (depending on duration of infusion) MRI performed within 4 hours (ideally within 2 hours) after completion of infusion relative to infusion end date/time; another MRI performed within 18-30 hours after completion of infusion prior to subject being discharged from the hospital
- g5 MRI performed as part of the scheduled follow-up visits on Days 30, 60, 90, 120 and then q8w thereafter until Day 360 / early termination. For patients who are progression free, MRIs will continue as per the institution's standard of care schedule until confirmed disease progression.
- g6 CT scan acquisition only required when no CT scan is available within 3 months of planned infusion
- h1 Females of child bearing potential only at Screening, Days 30 and Day 180
- h2 Hematology: hemoglobin, hematocrit, platelet count, white blood cell (WBC) count, and WBC differential;
 Serum chemistry: AST, ALT, lactate dehydrogenase (LDH), total bilirubin, indirect bilirubin, alkaline phosphatase, total protein, albumin, sodium, potassium, chloride, carbon dioxide, calcium, phosphorus, blood urea nitrogen (BUN), creatinine, uric acid, and glucose
- h3 Coagulation: prothrombin time (PT)/PTT/INR (PTT, corrected, if necessary)

Protocol # MDNA55-05 Version: v.6.1

CONFIDENTIAL

h4 Urinalysis: pH, specific gravity, protein, glucose, ketones, blood, leukocyte esterase, and nitrite. Microscopy required only to follow-up clinically significant abnormal findings

- 11 PK assessed at Screening (baseline), as soon as possible but not more than 1 hour following infusion end time, approximately 3 hours following completion of infusion and then (after the ~3 hour sample collection) every 6 hours ± 2 hours until 24 hours or until subject is discharged from the hospital (whichever occurs first) and at Day 14
- i2 Immunogenicity assessed at Screening (baseline) and at Days 14, 30, 120, 240, and 360/early termination
- i3 Pre-anesthesia blood draw (within 1 hour of subject be placed under anesthesia), this blood sample collection and processing will use a study specific sample collection kit and require immediate (same day) shipment to central laboratory

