7.5.2.4 End of CED Infusion (Day 1 - 2)

These procedures must be completed at the end of the CED infusion (see Section 6.3):

A standard 12 Lead ECG (triplicate assessment) will be performed immediately following

completion of the infusion (within 2 hours)

Version: v.6.1

MRI for final evaluation of drug distribution (with catheters maintained in place) will be performed within 4 hours (ideally within 2 hours) following completion of infusion

- o Removal of catheters and closure of incisions in accordance with institutional practice at bedside. NOTE: catheters are only removed after the end of infusion MRI is performed.
- Collection of blood samples for PK analysis as soon as possible but not more than 1 hour following infusion end time, approximately 3 hours following completion of infusion and then (after the ~3 hour sample collection) every 6 hours ± 2 hours until 24 hours or until subject is discharged from the hospital (whichever occurs first)
- Blood samples for hematology, serum chemistry, and coagulation (Section 7.2.1) shall be taken in parallel with either the PK blood collection that is performed within 1 hour following completion of infusion or the PK blood collection that is performed ~3 hours following completion of infusion.
- MRI performed within 18-30 hours after infusion end time to assess non-specific enhancement following the infusion
- Brief medical history and physical and neurological examinations including KPS, noting any changes since prior to study drug administration shall be performed when the subject is ambulatory prior to hospital discharge.
- Vital signs (pulse, respiratory rate, blood pressure and weight) taken when the subject is ambulatory prior to hospital discharge.
- Any AEs and new concomitant medications and/or changes to concomitant medications will be recorded throughout entire hospitalization period.

7.5.3 **Post-Treatment Follow-up Assessments**

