7.9 Pharmacokinetic Listing

Systemic exposure to MDNA55 is not expected following intra- and peritumoral infusion and circulating MDNA55 has not been detected in previous clinical studies. To continue to evaluate the potential of systemic exposure, plasma collected at screening (baseline), within 1 hour following infusion end time, ~3 hours following completion of infusion and then (after the ~3 hour sample collection) every 6 hours ± 2 hours until 24 hours and at Day 14.

PK data will be presented for the PK population in listing format by subject and sample collection time point.

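### No PK sample is scheduled during the 24–48 h infusion and the first may come up to 1 h after it ends, so the schedule can miss end-of-infusion exposure if plasma entry is fast and plasma half-life is short

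*Protocol*

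**What the plan says.** Protocol 7.2.3 gives the purpose: "To continue to evaluate the potential of systemic exposure, blood samples will be collected for analysis at the times indicated in Table 7". Table 7 marks PK at screening, at end of infusion and on Day 14. Its CED Infusion column has no PK mark.

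Footnote i1 places the first post-baseline draw "as soon as possible but not more than 1 hour following infusion end time" and the second about 3 h after the end. The rest follow "every 6 hours ± 2 hours until 24 hours or until subject is discharged from the hospital (whichever occurs first) and at Day 14". Protocol 7.5.2.4 repeats this among the end-of-infusion procedures ("Collection of blood samples for PK analysis as soon as possible but not more than 1 hour following infusion end time"), and SAP 7.9 agrees ("within 1 hour following infusion end time, ~3 hours following completion of infusion").

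Protocol section 3 sets the length of delivery: "The flow rate should be established such that the duration of infusion is at least 24 hours to a maximum of approximately 48 hours".

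SAP 5.5 has the 6 and 9 µg/mL subjects assayed first. If all their results are below the level of quantitation (BLQ), no one else is assayed unless a regulator asks. SAP 7.9 presents PK only as a listing by subject and sampling time point.

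**The concern.** If drug reaches plasma while the pump runs and is cleared quickly, plasma concentration is highest at the end of infusion and falls at once. A first draw as late as 1 h afterwards then measures a remnant, which may lie below the assay limit. The error is toward non-detection.

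The consequence is not confined to one subject's listing. Under SAP 5.5, a uniformly BLQ result in the two highest concentration groups closes the PK assessment. Such a result is informative only if the draws could have detected exposure. The documents supply none of the three figures needed to judge that: plasma half-life, rate of transfer from brain to plasma, and limit of quantitation.

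**Working it through.** The plan states no PK figure to reproduce, so the check asks what share of the true peak the scheduled draws would see.

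**Inputs from the documents.** Infusion length T = 24 or 48 h (Protocol section 3). Draws after the stop: up to 1 h, about 3 h, then 6-hourly, taken here as T+1, T+3, T+9, T+15 and T+21 h (footnote i1).

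**Assumptions.** Linear kinetics, constant rate, plasma half-life 10 min to 8 h, brain-to-plasma efflux half-life 0.5 to 24 h. None of these values comes from the documents.

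**Model A, direct entry into plasma.** During infusion C(t) ∝ 1 − exp(−kt), with k = ln 2 / half-life. C rises throughout, so the peak is at T. After the stop, the share of peak left at lag d is 0.5^(d / half-life):

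| Plasma half-life | 15 min lag | 1 h lag |
|---|---|---|
| 10 min | 35% | 0.5^6 = 1.6% |
| 30 min | 71% | 0.5^2 = 25% |
| 1 h | 84% | 0.5^1 = 50% |
| 2 h | 92% | 0.5^0.5 = 71% |
| 4 h | 96% | 0.5^0.25 = 84% |
| 8 h | 98% | 0.5^0.125 = 92% |

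**Model B, release from a brain depot.** The pump fills a depot that empties into plasma at rate k_b, and plasma clears at rate k_p. The step response is S(t) ∝ 1 − [k_p·exp(−k_b·t) − k_b·exp(−k_p·t)] / (k_p − k_b), and C(t) = S(t) − S(t−T) after the stop. The peak falls at infusion end or up to 9.7 h later.

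- Efflux half-life 2 h or more: the T+1 h value is 77% to 100% of peak.
- Efflux half-life 30 min: 37% of peak with a 10 min plasma half-life, 60% with 30 min, 75% with 1 h.

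**Re-timed first draw.** Replace T+1 h by T−0.5 h and keep the rest. The highest scheduled draw is then at least 97% of peak in every case of both models. The lowest value is 97.5% (T = 24 h, efflux 24 h, plasma 1 h). With the first draw at the 1 h limit, the corresponding range is 1.6% to 100%. In the slowest case (T = 24 h, efflux 24 h, plasma 8 h), the T−0.5 h draw alone gives 81%, adding T+3 h gives 93%, and adding T+9 h gives over 99%. The later draws must therefore stay.

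**Late rate cut.** Protocol 1.4.5 allows the rate to be halved. If it is halved for the last 4 h under model A, concentration at the stop is 0.5 + 0.5·0.5^(4 / half-life) of the earlier peak: 50%, 53% and 75% for half-lives of 0.5, 1 and 4 h. Neither first-draw time recovers that peak.

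**The case against.** The strongest reply is that the schedule already aims at the right moment. For a sustained or stepped-up infusion the peak is at infusion end or later, and the footnote asks for a draw as soon as possible, with 1 h as the outer limit. MDNA55 is a 53 kDa protein placed in tumor and brain (Protocol 1.2.3), so release from a depot is at least as plausible as direct entry, and then little is lost. The 1.6% figure needs direct entry, a 10 min half-life and a full hour's delay together. All of this stands, and it limits the point to *can miss*.

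Two stronger readings are tempting. A reader might infer that the trial never tests at the peak. The documents do not support this: under slow efflux the peak falls among the scheduled draws. A reader might also cite the catheter that Protocol 1.4.6 allows to be shut down. Real-time monitoring lasts about one hour (Table 6), so exposure from a leak closed then would largely be gone after a 24–48 h infusion. A pre-stop draw would miss it as well. That is a limit on interpretation, not an argument for re-timing.

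There are practical objections too. An infusion stopped early (Protocol 7.5.2.3) would lose a purely pre-stop sample, and the safety laboratory draws are tied to the within-1 h or ~3 h PK draw (Protocol 7.5.2.4). Both are right and are met in the fix. It is also true that SAP 7.2 already lists infusion end date and time, and that the expectation of no systemic exposure in Protocol 7.2.3 is accompanied by reference to earlier studies.

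**Conclusion.** The point holds in limited form. No PK sample is scheduled during delivery, and a first draw at the 1 h limit could see as little as 1.6% of peak or essentially all of it. Which applies depends on half-life, efflux rate and assay limit, none of them given in the protocol or SAP. The Investigator's Brochure or laboratory manual may hold them. The loss is substantial only with fast plasma entry, a plasma half-life of about 1 h or less, and a late draw.

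The SAP 5.5 rule is the reason to act, since a BLQ set from late draws could end the assays. Severity is low: PK is exploratory and only listed, and no efficacy result, power or error rate depends on it. The percentages rest on linear kinetics and a constant rate up to the stop.

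**What to change.** In Protocol Table 7 (footnote i1 and the PK row), Protocol 7.5.2.4, SAP Table 2 and SAP 7.9:

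- Take the first post-baseline PK sample in the last 30 minutes of infusion. If the infusion stops early or unexpectedly, take it immediately at the stop.
- Keep the ~3 h, 6-hourly and Day 14 draws.
- Pair the hematology, chemistry and coagulation samples with the pre-stop or the ~3 h draw (Protocol 7.5.2.4; SAP Table 2, footnote u).

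In SAP 7.9, list the actual draw time relative to infusion stop and the assay's limit of quantitation. Report BLQ results from subjects sampled under the present schedule as *not detected after end of infusion*, and read the SAP 5.5 rule in that light.

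The number of draws is unchanged. The cost is a protocol and SAP wording change, and subjects treated before and after it will have different first-sample times. Subjects have already been treated, and the documents do not say how many infusions remain. If none do, only the listing and wording changes can be applied, and they need no new samples.

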7.5.1 Pretreatment Period

7.5.1.1 Informed Consent

Each subject will provide signed informed consent and Health Insurance Portability and Accountability Act (HIPAA) authorization as per institutional and/or Institutional Review Board (IRB)/Independent Ethics Committee (IEC) guidelines and in accordance with the requirements of the International Council on Harmonization guidelines on Good Clinical Practice (ICH E6 GCP) and the principles of the Declaration of Helsinki. Major deviations may not be made from the informed consent provided by the Sponsor unless requested by the IRB/IEC. If translation of informed consent form (ICF) is required, the Sponsor will review a certified back-translation to ensure all elements are present. The IRB/IEC-approval document must be provided to the Sponsor or their representative for regulatory purposes.

Before a subject undergoes any study-related procedures or examinations, the Investigator or approved delegate will explain to each subject (or legal guardian) the nature of the study, its purpose, procedures, expected duration including the necessity to collect information about the subject's treatment and disease after completion of the scheduled last follow-up visit, and the potential benefits and risks of participation.

Subjects will be informed of their right to refuse to consent to the study or to withdraw from the study at any time without any change in the quality of their health care. Subjects will be provided with a copy of the IRB/IEC approved ICF and they will have sufficient time to consider the study information and ask any questions.

If a subject (or legal guardian) agrees to participate in the study, he/she (or legal guardian) will sign and date a statement indicating their informed consent. The statement will also be signed by the Investigator or approved delegate to indicate that he/she fully informed the subject and witnessed the freely provided consent. A copy of the signed ICF will be given to the subject, and a copy will be filed in the medical record. The original signed ICF will be kept on file with the Investigator's study records.

7.5.1.2 Screening Assessments (within 14 Days of Infusion)

Before a subject can be considered for entry into the study, the Investigator must receive the subject's clinical history, general laboratory results, specific radiological evaluations and diagnoses, and a chronology of all previous therapies for the treatment of GB, including outcomes,

Protocol # MDNA55-05 Version: v.6.1

from the referring physician. Subjects should have results from a previous histological diagnosis of initial primary (*de novo*) GB and a pre-study MRI scan providing radiological evidence of recurrence or progression.

A written and signed ICF and HIPAA authorization must be obtained before any study-specific assessments are initiated (See Section 7.5.1.1). The ICF can be signed in advanced of the 14 day screening period.

The following assessments must be carried out within 14 days before catheter placement:

- Screening MRI to assess radiologic eligibility criteria and catheter trajectory planning using iPlan® Flow Infusion planning software
 - Electronic image data transfer immediately following acquisition (< 4 hours)
- CT scan assessed during screening to ensure no prior skull defects or hardware that would preclude catheter placement (CT scan acquisition only required when no CT scan is available within 3 months of planned infusion)
 - Electronic image data transfer (should be concomitant with transfer of screening MRI)
- Verification that archived tumor tissue (from initial GB diagnosis) is available for retrospective biomarker analysis
- Complete medical and oncologic history, including history of prior surgical procedures and prior treatments, prior conditions, signs and symptoms and any residual/ongoing toxicity relating to prior treatment(s)
- Complete physical and neurological examinations, including height, weight, mental status, cranial nerves, motor and sensory examinations, and KPS
- Baseline signs and symptoms
- Vital signs (pulse, respiratory rate, weight and blood pressure)
- Standard 12-lead ECG (triplicate assessment)
- Hematology, serum chemistry, and coagulation (Section 7.2.1)
 - If the coagulation values are clinically significant, they must be repeated until within normal limits, unless subject is receiving therapeutic low molecular weight heparin

NOTE: Any test results outside of the reference ranges may be repeated at the discretion of the Investigator

- Collection of blood sample for Immunogenicity analysis (baseline)
- Collection of blood sample for PK analysis (baseline)

Concomitant medications and treatments will be recorded from 14 days before infusion (Day 0) until the Day 360 (or early termination) visit, and AEs will be recorded from the time of signing the informed consent document until the Day 360 (or early termination) visit.

In addition, a serum pregnancy test must be performed within 14 days before infusion (Day 0) for all female subjects of childbearing potential.

While the above assessments are being carried out, screening MRI will be subject to review by CED experts pertaining to evaluation of suitability of tumor for convection. The screening MRI will also be sent to an independent central assessment of objective radiologic tumor characteristics.

Subjects will be approved for enrollment by the Medical Monitor following comprehensive review all screening results.

Following approval of subject for enrollment, Investigator/site will be notified and preliminary pretreatment catheter trajectory planning using CT scan and screening MRI (registered with iPlan® Flow Infusion planning software) can ensue (see Section 6.3 for catheter placement guidelines).

NOTE: use of iPlan® Flow software is required for catheter trajectory planning.

7.5.2 Treatment Period

7.5.2.1 Pre-operative study Procedures within 24 hours of catheter placement

Within 24 hours prior to catheter placement, subjects will undergo the following procedures and assessments:

- Pre-operative Planning MRI
 - Pre-operative planning MRI can be performed in one or two MRI exams as required, based on local capabilities; Timing of planning images to support catheter trajectory planning is described in Table 6.
 - Planning MRI images will be registered with iPlan® Flow Infusion planning software to support finalization of catheter trajectory plan.

• NOTE: use of iPlan® Flow software is required for catheter trajectory planning.

 Brief medical history and physical and neurological examinations including KPS, noting/recording any changes since screening;

- Vital Signs (pulse, respiratory rate, weight and blood pressure)
- Review of Baseline Signs and Symptoms noting/recording any changes or new signs/symptoms since screening in medical history; Any changes to concomitant medications will also be recorded;
- Treatment Plan (study specific source worksheet) will be completed and reported to hospital pharmacy for dispensing infusate at the time required on Day 0.

7.5.2.2 Study Drug Administration (Day 0)

On Day 0 subjects will undergo the following procedures and assessments:

- Pre-anesthesia blood draw
 - Blood sample collection and processing will use a study specific sample collection kit and require immediate shipment to the central laboratory
- Just prior to catheter insertion, core tumor biopsy samples (at least 3 cores) will be collected, if the neurosurgeon determines it is possible to harvest viable tumor tissue from along the planned trajectory of the CED catheter(s)
 - Biopsy sample tissue collection and processing will use a study specific sample collection kit and require immediate shipment to the central laboratory
- Catheter placement and infusion (see Section 6.3 for outline of surgical procedures and instructions for study drug administration via CED with real-time imaging)
 - See Table 1 for example of mandatory antibiotic / H-2 antagonist therapy and Table 2 and Table 3 for optional dexamethasone and mannitol therapy for management of raised intra-cranial pressure (ICP).
 - Throughout entire surgical workflow for catheter placement and infusion vital signs (pulse, respiratory rate and blood pressure) will be performed according to institutional best practice; study specific vital signs check points during the surgical workflow are as follows:

Version: v.6.1

Vital signs taken prior to initiation of anesthesia

 Vitals signs taken following placement of all catheters but prior to patient being loaded into MRI machine for the real-time infusion monitoring

segment

Vital signs taken approximately 1 hour post initiation of infusion

Site will record any abnormal vitals observed at any time during surgical

vital signs monitoring as unscheduled findings

• Any AEs experienced or concomitant medications received during the catheter placement

procedure or during the infusion will be recorded in the subjects' medical records and EDC

system

NOTE: Subjects will likely be admitted to hospital for 2 nights.

